# PROTOCOL SYNOPSIS

#### Gilead Sciences, Inc. [name]

Study Title:	A Phase 3b, Multicenter, Randomized, Open-Label Study to Investigate the Efficacy and Safety of Ledipasvir/Sofosbuvir Fixed-Dose Combination for 12 Weeks in Subjects with Chronic Genotype 2 HCV Infection
IND Number: EudraCT Number: Clinical Trials.gov Identifier:	This is a non-IND study Not Applicable Not Available
Study Centers Planned:	Approximately 40 centers in Japan.
Objectives:	
 
The primary objectives of this study are follows:
 
To evaluate the antiviral efficacy of therapy with ledipasvir/sofosbuvir (LDV/SOF) fixed-dose combination (FDC) as measured by sustained virologic response 12 weeks after cessation of treatment (SVR12)
 

	
 
To evaluate the safety and tolerability of each regimen as assessed by review of the accumulated safety data
 
The secondary objectives of this study are as follows:
 
To determine the proportion of subjects who attain SVR at 4 and 24 weeks after cessation of treatment (SVR4 and SVR24)
 
To evaluate the proportion of subjects with virologic failure
 
To evaluate the kinetics of circulating HCV RNA during treatment and after cessation of each treatment regimen
 

	
 
To evaluate the emergence of viral resistance to SOF and LDV during treatment and after cessation of treatment
 
Exploratory objectives of this study are:
 

Study Design:	This is a multicenter, randomized, open-label study in treatment-naïve and treatment-experienced adults with chronic genotype 2 HCV infection.
	Cohort 1: Approximately 200 subjects will be randomized in a 1:1 ratio to one of the following two treatment groups:
	• LDV/SOF FDC tablet (90/400 mg) once daily for 12 weeks
	• SOF tablet (400 mg) once daily and RBV (600-1000 mg daily as a divided dose) for 12 weeks
	At least 20 subjects will have Child-Pugh-A compensated cirrhosis. Approximately 50% of subjects will be treatment-naïve and 50% will be treatment-experienced.
	Randomization will be stratified by cirrhosis status (presence/absence) and prior treatment experience (treatment-naïve/treatment-experienced).
	Cohort 2: Up to 25 subjects who are ineligible or intolerant for RBV therapy will receive LDV/SOF FDC tablet (90/400 mg) once daily for 12 weeks. Approximately 2 subjects will have Child-Pugh-A compensated cirrhosis.
Number of Subjects Planned:	Approximately 225 subjects
Target Population:	Treatment naïve and treatment experienced, chronic genotype 2 HCV infected adults
Duration of Treatment:	Subjects will be treated for 12 weeks.
Diagnosis and Main Eligibility Criteria:	Chronic genotype 2 HCV-infected male and non-pregnant/non-lactating female subjects, aged 20 years or older, treatment naïve or treatment-experienced. At least 20 subjects in Cohort 1, and approximately 2 subjects in Cohort 2 will have Child-Pugh-A compensated cirrhosis. In Cohort 2 subjects must be ineligible or intolerant of RBV.

Study Procedures/ Frequency:	Screening assessments will be completed within 28 days prior to the Day 1 visit. The screening window can be extended up to 42 days in extenuating circumstances, including the need for a liver biopsy or additional HCV genotyping (if initial testing is inconclusive). Study visits will occur at Screening, Day 1, and on-treatment at the end of Weeks 1, 2, 3, 4, 5, 6, 8, 10, and 12. Following the last dose of study medication, all subjects will complete 4-Week, 12-Week and 24-Week Posttreatment Visits.
	Screening assessments will include medical history, physical examination, height, weight, vital signs, 12-lead electrocardiogram (ECG), adverse events (AEs) related to screening procedures, concomitant medications, liver imaging to exclude hepatocellular carcinoma (HCC) within 6 months for non-cirrhotics and within 4 months for cirrhotics, safety laboratory tests (including hematology, chemistry, coagulation, urinalysis), HCV RNA, serum $\beta$ -hCG (females of child bearing potential only), HCV genotype, host IL28B genotype, serology (HIV, HCV, HBV), hemoglobin A1c (HbA1c), and assessment of the presence or absence of cirrhosis (including FibroTest ® ).
	On-treatment assessments include physical examination, weight, vital signs, 12-lead ECG, AEs, concomitant medications, pregnancy prevention counseling, review of study drug adherence and drug accountability, study medication dispensing, safety laboratory tests (including hematology, chemistry, coagulation, urinalysis), HCV RNA, viral RNA sequencing/phenotyping sample, urine pregnancy tests (females of child bearing potential only).
	Posttreatment assessments include physical examination, weight, vital signs, AEs and concomitant medications, pregnancy prevention counseling, safety laboratory tests (including hematology and chemistry), HCV RNA, viral RNA sequencing/phenotyping, and urine pregnancy tests (females of childbearing potential only).
	For subjects who provide their additional and specific consent, a single blood sample will be collected at the Day 1 visit for human genomic testing (this sample may be drawn after Day 1, if necessary).
	Health Related Quality of Life (HRQoL) Survey will be conducted at Day 1, On-treatment Weeks 4, 8, and 12, Early Termination (if applicable), and Posttreatment Week 4, 12, and 24.
	Archive plasma samples will be collected at each on-treatment and posttreatment study visit for potential future testing.

Test Product, Dose, and Mode of Administration:	1. Ledipasvir/sofosbuvir (HARVONI ® , LDV/SOF) is manufactured as a FDC tablet, consisting of 90 mg LDV and 400 mg SOF, for oral administration. Subjects will take 1 tablet daily for 12 weeks.
	2. Sofosbuvir (SOVALDI ® , SOF) is manufactured as a 400mg tablet for oral administration. Subjects will take 1 tablet daily for 12 weeks.
	3. Ribavirin (REBETOL ® , RBV) is manufactured as a 200mg capsule. Subjects will take weight-based RBV every day (600-1000 mg/day in a divided daily dose) in accordance with RBV product labeling. The morning dose of RBV will be taken with the SOF tablet and with food. The evening dose of RBV will be taken alone with food. Ribavirin dose reductions and modifications will be performed according to the approved RBV labeling.
Reference Therapy, Dose, and Mode of	None

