#### 6.3. Treatment Assessments (±3 days)

On-treatment visits will be performed at the end of Weeks 1, 2, 3, 4, 5, 6, 8, 10, and 12.

Study medication will be reconciled at every post-Day 1 visit by the investigator in order to monitor the subject's adherence with the medication regimen.

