### **3.6. Missing Data and Outliers**

#### **3.6.1. Missing Data**

In general, missing data will not be imputed unless methods for handling missing data are specified.

For missing last dosing date of study drug, imputation rules are described in Section 3.8.1. The handling of missing or incomplete dates for adverse event (AE) onset is described in Section 7.1.5.2, and for prior and concomitant medications in Section 7.4.

For analyses of categorical HCV RNA data, missing posttreatment HCV RNA data will have the missing data imputed. Missing on-treatment HCV RNA will have the missing data imputed up to the time of the last dose (for on-treatment displays). If the study day associated with the last dosing date is greater than or equal to the lower bound of a visit window, and the value at the visit is missing, the value will be imputed. If the study day associated with the last dosing date is less than the lower bound of a visit window then the on-treatment value at that visit will remain missing.

If an HCV RNA data point is missing and is preceded and followed in time by values that are “< lower limit of quantitation (LLOQ) target not detected (TND)”, then the missing data point will be set to “< LLOQ TND”. If a data point is missing and preceded and followed by values

that are “< LLOQ detected”, or preceded by “< LLOQ detected” and followed by “< LLOQ TND”, or preceded by “< LLOQ TND” and followed by “< LLOQ detected”, then the missing value will be set to “< LLOQ detected”. In these situations the data point will be termed a bracketed success; otherwise, the data point will be termed a bracketed failure (ie,  $\geq$  LLOQ detected). If a data point is missing and is not bracketed, the missing data point will also be termed a failure (ie,  $\geq$  LLOQ detected) except for SVR24, which will be imputed according to SVR12 status. Success for SVR12 who have no further HCV RNA measurements collected will be counted as a success for SVR24 due to the high correlation between these 2 endpoints.

For the analyses of continuous HCV RNA efficacy data, when and only when a missing HCV RNA value is imputed as < LLOQ TND or < LLOQ detected according to the imputation rule described above, the corresponding continuous value will be imputed to LLOQ - 1 IU/mL. No other imputation will be performed for continuous HCV RNA data.

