### **3.8. Visit Windows**

#### **3.8.1. Definition of Study Day**

Study day is the day relative to the date of the first dose of study drug. Study Day 1 will be defined as the day of first dose of study drug administration.

Study day will be calculated from the date of first dose of study drug administration and derived as follows:

- For postdose study days: Assessment Date – First Dose Date + 1
- For days prior to the first dose: Assessment Date – First Dose Date

The last dose date for an individual study drug will be the end date on study drug administration eCRF for the record where the “subject permanently discontinued” flag is ‘Yes’. The last dose date will be defined as the maximum of the last dose dates of individual study drugs in a treatment group.

If there are subjects for whom the date of last study drug is unknown due to the reason that the subject was lost to follow-up and not able to be contacted, the date of last dose will be estimated using the maximum of nonmissing study drug start or stop dates, visit dates and laboratory collection dates (posttreatment visits and unscheduled visits are not included).

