### **3.8.3. Selection of Data in the Event of Multiple Records in an Analysis Window**

Depending on the statistical analysis method, single values may be required for each analysis window. For example, change from baseline by visit usually requires a single value, whereas a time-to-event analysis would not require 1 value per analysis window.

If multiple valid nonmissing numeric observations exist in an analysis window, records will be chosen based on the following rules if a single value is needed:

- For baseline, the last available record on or prior to the date of the first dose of study drug will be selected. If there are multiple records with the same time or no time recorded on the same day, average (arithmetic mean) will be used for the baseline value. If multiple ECG measurements occur on the same day prior to first dose of any study drug, the average will be used as baseline value for continuous data, regardless of the timing of these multiple ECG measurements.
- For postbaseline visits:
  - The record closest to the nominal day for that visit will be selected except for HCV RNA posttreatment follow-up visits, for which the latest record in the analysis window will be selected.
  - If there are 2 records that are equidistant from the nominal day, the later record will be selected.
  - If there is more than 1 record on the selected day, the average will be taken, unless otherwise specified.

If multiple valid nonmissing categorical observations exist in a window, records will be selected as follows:

- For baseline, the last available record on or prior to the date of the first dose of study drug will be selected. If there are multiple records with the same time or no time recorded on the same day, the value with the lowest severity will be selected (eg, normal will be selected over abnormal). If multiple ECG measurements occur on the same day prior to the first dose of any study drug, the value with the lowest severity will be selected regardless of the timing of these multiple ECG measurements.
- For postbaseline visits, follow the same rules described above for postbaseline numeric observations, except that if there are multiple records on the same day, the most conservative value will be selected (eg, abnormal will be selected over normal).

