##### **4.2.1. Duration of Exposure to Study Drug**

Total duration of exposure to study drug will be defined as last dose date minus first dose date plus 1, regardless of any temporary interruptions in study drug administration, and will be expressed in weeks using up to 1 decimal place (eg, 4.5 weeks).

The total duration of exposure to study drug will be summarized using descriptive statistics (n, mean, SD, median, Q1, Q3, minimum, and maximum) and using the number (ie, cumulative counts) and percentage of subjects exposed through the following time periods: baseline (Day 1), Week1 (Day 7), Week 2 (Day 14), Week 3 (Day 21), Week 4 (Day 28), Week 5 (Day 35), Week 6 (Day 42), Week 8 (Day 56), Week 10 (Day 70), and Week 12 (Day 84). A 3-day window will be applied to the last planned on-treatment visit to match with the protocol-

specified visit window (ie, the number of subjects exposed through week 12 will be calculated as the number of subjects who were exposed to study drug for at least 81 days). Summaries will be provided by treatment group within each cohort for the Safety Analysis Set.

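### SAP Table 3-1 pairs nominal days at Day 7k with Week 1 to 6 boundaries built around Day 7k+1, so a permitted visit three days early at Weeks 2 to 6 is filed under the previous week (minor)

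*Protocol*

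**What the plan says.** The Protocol Synopsis schedules visits "on-treatment at the end of Weeks 1, 2, 3, 4, 5, 6, 8, 10, and 12". The heading of Protocol 6.3, "Treatment Assessments (±3 days)", gives the tolerance, and the Study Procedures Table repeats it. The protocol numbers no visit by study day.

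SAP 3.8.1 fixes the count: "Study Day 1 will be defined as the day of first dose of study drug administration". SAP 4.2.1 maps weeks to days as "Week 2 (Day 14), Week 3 (Day 21), Week 4 (Day 28), Week 5 (Day 35)". It adds "A 3-day window will be applied to the last planned on-treatment visit", so that exposure through Week 12 means subjects "who were exposed to study drug for at least 81 days". Table 3-1 in SAP 3.8.2 uses the same nominal days, with windows of 2-11, 12-18, 19-25, 26-32, 33-39 and 40-49 for Weeks 1 to 6.

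When several on-treatment records share a window, SAP 3.8.3 says: "The record closest to the nominal day for that visit will be selected". When a categorical HCV RNA value is missing, SAP 3.6.1 sets it to below LLOQ if the values before and after it are below LLOQ; "otherwise, the data point will be termed a bracketed failure". SAP 6.2.2 excludes missing continuous HCV RNA unless it is bracketed in that way.

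**The concern.** With the first dose on Day 1, the end of Week k is Day 7k, which is also the SAP's nominal day. A tolerance of 3 days should then give windows starting on Days 11, 18, 25, 32 and 39 for Weeks 2 to 6. Table 3-1 starts them one day later, so one permitted day per visit belongs to the week before.

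What is at stake is the by-visit on-treatment reporting: the secondary endpoint of HCV RNA below LLOQ by visit, HCV RNA change from baseline, and the by-visit laboratory and vital-sign summaries. The last group includes hemoglobin over Weeks 2 to 6, in a trial with a ribavirin comparator.

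**Working it through.** **Inputs.** Visit weeks and tolerance: Protocol Synopsis and 6.3. Day count: SAP 3.8.1. Nominal days and windows: SAP Table 3-1. Record selection: SAP 3.8.3. Missing HCV RNA: SAP 3.6.1 and 6.2.2.

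**1. Reproducing the plan's limits.** Take each boundary as the midpoint between adjacent nominal days.

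- Nominal days 7k: the midpoint of 7 and 14 is 10.5, so Week 2 starts on Day 11. Weeks 2 to 6 start on 11, 18, 25, 32 and 39. Table 3-1 has 12, 19, 26, 33 and 40. Not reproduced.
- Nominal days 7k+1: the midpoint of 8 and 15 is 11.5, so Week 2 starts on Day 12. With ties going to the later visit, Weeks 2 to 12 start on 12, 19, 26, 33, 40, 50, 64 and 78. Every lower limit in Table 3-1 is reproduced.

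The two parts of the table follow different conventions.

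**2. Permitted days against windows** (nominal day − 3 to nominal day + 3):

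| Visit | Nominal day | Permitted days | Table 3-1 window | Permitted day placed elsewhere |
|---|---|---|---|---|
| Week 1 | 7 | 4-10 | 2-11 | none |
| Week 2 | 14 | 11-17 | 12-18 | Day 11, to Week 1 |
| Week 3 | 21 | 18-24 | 19-25 | Day 18, to Week 2 |
| Week 4 | 28 | 25-31 | 26-32 | Day 25, to Week 3 |
| Week 5 | 35 | 32-38 | 33-39 | Day 32, to Week 4 |
| Week 6 | 42 | 39-45 | 40-49 | Day 39, to Week 5 |
| Week 8 | 56 | 53-59 | 50-63 | none |
| Week 10 | 70 | 67-73 | 64-77 | none |
| Week 12 | 84 | 81-87 | 78 onward | none |

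**3. Which record survives.** The early record lies 4 days from the previous nominal day (for example 25 − 21 = 4). A previous visit inside its tolerance and its own window lies at most 3 days away, so the early record loses. If each of the 7 permitted days is equally likely (an assumption), then given a visit 3 days early:

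- Its record is dropped always at Week 2, and in 6/7 = 85.7% of cases at Weeks 3 to 6. In the other 1/7 the previous visit was also 3 days early, and the record is reported under the wrong week.
- Its own window is empty in 6/7 of cases at Weeks 2 to 5. In the other 1/7 the next visit, also 3 days early, fills it. At Week 6 the window is always empty, because the earliest permitted Week 8 day is 53.

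**4. Share affected.** The documents do not say how visit days spread.

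- No visits 3 days early: 0%.
- 3% of visits 3 days early (assumed): 0.03 × 225 × 5 ≈ 34 of 1,125 Week 2 to 6 visits.
- Even spread (assumed): 1/7 = 14.3%, or 1,125 / 7 ≈ 161 visits. Windows are then empty for 1/7 × 6/7 = 12.2% of subjects at Weeks 2 to 5, and for 14.3% at Week 6.

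**5. Effect on the percentage below LLOQ.** This depends on how SAP 3.6.1 is read. Suppose Week 3 on Day 21 is ≥ LLOQ, the Week 4 visit on Day 25 is < LLOQ, and Week 5 is < LLOQ. Week 4 is empty.

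- If the neighbours are the values assigned to adjacent windows, they are ≥ LLOQ and < LLOQ, and Week 4 becomes a failure.
- If the neighbours are the values before and after in time, Day 25 is the preceding value, and Week 4 is a success.

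For illustration, 100,000 subjects were simulated with an assumed 55%, 80% and 93% below LLOQ by Days 14, 21 and 28, and assumed values at other days. On the window reading, the reported percentage at Weeks 2, 3 and 4 is too low by about 1.7, 1.0 and 0.6 points (even spread) or 0.5, 0.4 and 0.2 points (3% early). On the in-time reading there is no shortfall. The result is at most about 0.6 points too high with even spread and about 0.03 points with 3% early, because the next week's early visit sometimes fills the window.

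**The case against.** The strongest reply is that the limits may be right and the nominal days wrong. A subject who returns on the same weekday as Day 1 is seen on Day 7k+1, and the current windows then misplace no permitted visit. Recentring on Day 7k would create the mirror image: visits 3 days late at Weeks 1 to 5 (Days 11, 18, 25, 32 and 39) would move to the next week, again 1/7 of visits under even spread. This stands as a reason to confirm the scheduling convention before editing. It does not rescue the table, because the nominal-day column and the week-to-day list in SAP 4.2.1 both use 7k, and no section states 7k+1.

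The 81-day rule is weaker support for 7k than it looks. It counts exposure, not visit day: a visit due on Day 85 but held on Day 82, with the last dose the day before, also gives 81 days.

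A reader might infer that measured results below LLOQ will be turned into failures, so that on-treatment response is understated. The documents do not support that as a firm statement. SAP 3.6.1 speaks of values before and after in time and does not mention window-assigned values. Read literally, the early result can itself serve as the preceding value.

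A reader might also infer that safety data are lost. Only the by-visit descriptive summaries lose them. All laboratory results are listed (SAP 7.2), treatment-emergent graded abnormalities use any postbaseline time point (SAP 7.2.2.1), and the hemoglobin counts below 10 and 8.5 g/dL use any postbaseline visit (SAP 7.2.1).

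**Conclusion.** Table 3-1 is internally inconsistent, and the point holds as a minor one. On the SAP's stated nominal days, one of seven permitted days at each of Weeks 2 to 6 is assigned to the previous week. The record is then usually dropped and its own week usually left empty. An empty week is imputed for categorical HCV RNA, excluded from continuous HCV RNA unless bracketed, and absent from by-visit laboratory and vital-sign summaries.

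The affected share runs from 0% to about 14% of Week 2 to 6 visits; the upper figure rests on the assumed even spread. Neither the size nor the direction of any bias in the percentage below LLOQ can be fixed from the documents, because both depend on visit timing, viral kinetics and the reading of SAP 3.6.1.

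SVR12 and the non-inferiority test use the posttreatment windows of Table 3-2 and are unaffected. Virologic failure is defined in SAP 6.2.1 on successive values without reference to Table 3-1. The same windows apply to both arms, and SAP 6.2.2 plans no between-group test of on-treatment results by visit.

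**What to change.** Confirm with the sponsor how on-treatment visits are scheduled, then put both parts of Table 3-1 on that convention before the SAP is finalized.

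- On Day 7k, as the SAP states: Week 1 = 2-10, Week 2 = 11-17, Week 3 = 18-24, Week 4 = 25-31, Week 5 = 32-38, Week 6 = 39-49, with Weeks 8, 10 and 12 unchanged. Every permitted day then falls in its own window. This changes ten limits.
- If visits are confirmed to be due on Day 7k+1: keep the limits and change the nominal days to 8, 15, 22, 29, 36, 43, 57, 71 and 85.

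In the same edit, one sentence in SAP 3.6.1 could say whether bracketing uses observed values in time order or window-assigned values.

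The cost is one table and the matching programming constants. No new data and no protocol amendment are needed.

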# Criteria for Evaluation:

Administration:

Safety:	AEs and safety laboratory tests will be collected throughout the study.
Efficacy:	Efficacy will be evaluated using scheduled assessments of HCV RNA performed using Ampliprep ® TaqMan ® HCV Test, v2.0.
Statistical Methods:	The primary efficacy endpoint is SVR12 in all randomized/enrolled and treated subjects.
	Cohort 1: The primary analyses will consist of a non-inferiority test of treatment LDV/SOF FDC for 12 weeks versus SOF+RBV for 12 weeks at the 0.05 significance level.
	Non-inferiority will be assessed using the conventional confidence interval approach, and a clinically meaningful non-inferiority margin of 10% will be applied. The two-sided 95% confidence intervals will be constructed using stratum-adjusted Mantel-Haenszel (MH) proportions, stratified by the randomization stratification factors (ie, cirrhosis status and prior treatment experience).
	A sample size of 100 per treatment group will provide over 90% power to establish non-inferiority in the SVR12 rates between the two groups. It is based on the assumptions that the clinically meaningful non- inferiority margin is 10%, both groups have a SVR12 rate of 96%, and the significance level is 0.025 one-sided.
	Cohort 2: No statistical hypothesis testing will be performed. A point- estimate with two-sided 95% exact confidence interval using the binomial distribution (Clopper-Pearson method) will be constructed for the SVR12 rate.

The secondary efficacy endpoints include SVR measured at 4 and 24 weeks after discontinuation of study drug (SVR4 and SVR24); proportion of subjects who have HCV RNA < LLOQ by visit while on study treatment; absolute and change from baseline in HCV RNA through end of treatment; and virologic failure.

This study will be conducted in accordance with the guidelines of Good Clinical Practice (GCP) including archiving of essential documents.

